2 STUDY OBJECTIVE

This study is being conducted to evaluate the efficacy and safety of SB206 12% QD for the treatment of MC.

3 STUDY ENDPOINTS

The following endpoints will be assessed during the study.

3.1 Primary Efficacy Endpoint

- Proportion of subjects with complete clearance of all treatable MC at Week 12

3.2 Secondary Efficacy Endpoint

- Proportion of subjects with complete clearance of all treatable MC at Week 8

3.3 Exploratory Endpoints

- Proportion of subjects who have a recurrence of MC after the first visit at which complete clearance was observed
- Proportion of subjects developing scar(s) after clearance of lesion(s) at each visit (Weeks 4, 8, 12, 24)
- Proportion of subjects with complete clearance of all treatable MC at each visit (Weeks 2, 4)

- Proportion of subjects achieving at least a 75% reduction from Baseline in the number of all treatable MC at each visit (Weeks 2, 4, 8, 12)
- Change from baseline of the composite score from age-matched (at baseline) Dermatology Life Quality Index (DLQI) assessment at Week 12 at Week 12
- Subject-reported spread to household members as measured by any new occurrence of MC in household members of subjects at each visit (Weeks 2, 4, 8, 12)
- Mean change from Baseline in number of treatable MC at each visit (Weeks 2, 4, 8, 12)
- Mean percent change from Baseline in number treatable MC at each visit (Weeks 2, 4, 8, 12)
- Time to complete clearance of all treatable MC

3.4 Safety Endpoints

Safety assessments will be performed at scheduled timepoints throughout the study and include physical examination, urine pregnancy test, Beginning of the End (BOTE) Inflammation Score, Local Skin Reaction Scores (LSRs), concomitant medications, and adverse events (including scarring/keloid scarring).

4 STUDY PLAN

4.1 Study Design

This is a Phase 3 multi-center, randomized, double-blind, vehicle-controlled, parallel group study to be conducted in approximately 340 subjects with MC. After obtaining informed consent/assent, subjects who satisfy entry criteria will be randomized 2:1 (active:vehicle). Subjects receiving current treatment for MC at the time of the Screening Visit will enter a wash out period of up to 14 days prior to randomization. In the event no wash out period is required. Screening and Baseline visit activities may be combined into a single visit. At randomization, subjects will be stratified into four strata corresponding to the cross-classification of household number of randomized subjects (1 subject per household vs 2 subjects per household) and investigator type (dermatologist vs other). Households randomizing 2 subjects will receive the same treatment assignment for both subjects. Up to two subjects from the same household may be randomized on the same day, if both individually meet all inclusion/exclusion criteria. For subjects in the same household, Screening can occur on different days; however, the Baseline visit must occur on the same day.

Subjects or their caregivers will apply SB206 12% or Vehicle Gel once daily for a minimum of 4 weeks and up to 12 weeks to all lesions identified at Baseline and new treatable lesions that arise during the course of the study. Subjects or their caregivers will continue to treat the area until the next scheduled visit even if the lesion(s) clear. If the investigator determines all lesions are cleared at a clinic visit, the treatment may stop. At Weeks 2, 4, and 8, the investigator will count and record the number of active (raised, treatable) molluscum lesions per body area. The investigator will also determine if new lesions have occurred since the last visit, and the subject or caregiver will be instructed by the investigator to re-initiate treatment. If treatment is stopped due to clearance, subjects will continue regularly scheduled visits through Week 24.

Subjects will visit the clinic at Screening/Baseline, Week 2, Week 4, Week 8, Week 12, and Week 24. Subjects will be contacted via phone on Day 2 to collect subject information on early dose reactions. At Weeks 16 and 20, subjects will be contacted via phone to capture information regarding MC recurrence and AEs; at Week 24, the subject will be seen at the site for a final study visit. Subjects who discontinue the study prior to the Week 12 visit due to adverse events or other reasons will be asked to complete the Week 12 visit assessments; this will be recorded as an Early Termination (ET1) visit. No study drug treatment will be provided after the Week 12 visit. Subjects who discontinue from the study after Week 12 but prior to Week 24 will be asked to come to the site to complete Week 24 assessments; this visit will be recorded as an ET2 visit.

Safety assessments include BOTE Inflammation Scores, Local Skin Reaction Scores (LSRs), adverse event collection, including scarring/keloid and urine pregnancy tests (UPTs). Safety assessments will be completed at specified site visits through Week 12. After Week 12, safety information for ongoing AEs and new AEs will be collected, along with information regarding MC recurrence. For the purpose of this study, a recurrence of MC will be documented as an AE.

Inflammatory reactions around the MC has been associated with imminent resolution of MC (sometimes referred to as “beginning-of-the-end” [“BOTE”] sign). The investigator (or designated evaluator) will assess the presence and overall degree of inflammatory reactions at MC lesions at Baseline (pre-dose) and Weeks 2-12. In most cases, clinical features can differentiate between BOTE and LSR. BOTE may be associated with itch, but not pain. BOTE is usually asymptomatic, self-limited, localized to individual MC lesions, and does not require discontinuation of study treatment or additional treatment. LSR is generally more diffuse, associated with significant itch or tenderness, may necessitate discontinuation of study treatment and may need treatment for symptomatic relief (e.g. a topical corticosteroid or topical anesthetic). For very severe LSR, systemic corticosteroids may be considered. Investigators will assess the treatment area at each scheduled visit and use their medical judgement to differentiate between BOTE and LSRs. BOTE Inflammation Score and LSR score will be recorded at each visit. BOTE should not be considered an AE. When LSRs are clinically significant at the application site, the Investigator should report the condition as AE(s).

At Baseline (30 min. post-dose) and Weeks 2 through Week 12 the evaluators will rate LSRs on individual features including erythema, flaking/scaling, crusting, swelling, vesiculation/pustulation, and erosion/ulceration using the BOTE Inflammation Score ([Section 7.2.3](#)).

Local Skin Reaction (LSR) Scores

Clinically significant LSRs reported as AEs and/or subject reported intolerance (i.e. itching, pain) may result in an investigator-directed temporary treatment hold (drug holiday), and topical corticosteroids may be used to treat LSRs for up to 2 weeks. If a drug holiday is prescribed, Investigational product (IP) will still be dispensed at the clinic visit to ensure the subject may resume dosing prior to the next clinic visit. The subject may reinitiate study drug treatment prior to the next scheduled visit. Upon re-initiation of study drug treatment, if a subject develops worsening LSRs, allergic contact dermatitis may be suspected. The investigator may take photographs of the suspected allergic contact dermatitis and discuss possible confirmation of allergic contact dermatitis with the CRO medical monitor. The investigator should also discuss necessity of patch testing with the subject/caregiver. The investigator will then discontinue the subject from study drug treatment and treat the area(s) with corticosteroids for up to 2 weeks. If the subject provides consent/assent, the investigator will consult the clinical research organization (CRO) medical monitor to implement the process for patch testing.

Adverse events will be assessed and collected after the initiation of study drug treatment through the end of the subject's last visit. Treatment-related adverse events will be followed up until resolution or up to one year after last treatment, whichever occurs earlier.

Scar formation will be assessed starting at the Week 4 visit through Week 12 and again at Week 24. The investigator will map locations of the molluscum lesions at Baseline. Additional lesions identified through Week 12 will be added to the map. Using the map as a guidance, the investigator will assess the treated areas for scar/keloid formation. MC lesions may resolve with pitted scars (indentation), and the small scars that maintain original MC size (<5 mm) and less than 1 mm in depth will heal over time. Any pitted scars <5 mm in diameter and <1 mm in depth will not be considered AEs since these are considered part of the normal healing process. . If a scar is larger than 5 mm in diameter or greater than 1 mm in depth, this will be considered an adverse event for the purposes of this study. In addition, keloid/hypertrophic scars will also be recorded as adverse events.

If a subject's treatment is discontinued by the investigator or the subject because of an AE, that AE should be indicated as the reason for treatment discontinuation. All subjects will be encouraged to remain in the study throughout the 24-week study duration.

In the event of suspected allergic contact dermatitis, photographs may be taken of the affected area(s) and transmitted to the CRO medical monitor for review prior to initiating patch testing.

When approximately 200 subjects (cumulative across studies NI-MC302 and NI-MC302) have completed 4 weeks of treatment, a Data Safety Monitoring Board (DSMB) will review all available unblinded safety data (including completed patch testing results).

Table 1: Schedule of Assessments

	Screening	Treatment					
	Screening ¹ (Day -14 to Day 1)	Visit 1 ¹ Baseline (Day 1)	V2 Telephone Contact (Day 2)	Visit 3 ² Week 2 (Day 15 ±3)	Visit 4 ² Week 4 (Day 29 ±5)	Visit 5 ² Week 8 (Day 57 ±5)	Visit 6 ² Week 12/ ET1 (Day 85 ±5)
Informed Consent (Assent)	X						
Demographics	X						
Medical and Medication History	X						
Lesion Count or Recurrence	X	X		X	X	X	X
Physical Exam		X					X
Urine Pregnancy Test ³	X	X			X	X	X
BOTE Inflammation Score ⁴		X (pre-dose)		X	X	X	X
Local Skin Reactions (LSR) (post-dose) ⁴		X		X	X	X	X
Scarring/Keloid Assessment					X	X	X
DLQI/CDLQI ⁵		X					X
Review of Inclusion/Exclusion Criteria	X	X					
Drug Dispensed		X			X	X	
Dispense Subject Diary		X		X	X	X	
Review Subject Application Instructions		X		X	X	X	
In Clinic Study Drug Application ⁶		X		X	X	X	X
Review Study Drug Compliance				X	X	X	X
Collect Study Drug					X	X	X
Collect Subject Diary				X	X	X	X
Record Adverse Event (AE) and Concomitant Medication (CM) Changes ⁷		X	X	X	X	X	X

	Safety Follow-up		
	Visit 7 ² Week 16 Telephone Contact (Day 113±5)	Visit 8 ² Week 20 Telephone Contact (Day 141±5)	Visit 9 ² Week 24/ ET2 (Day 169±5)
Scarring/Keloid Assessment			X
Record Adverse Event (AE) and Concomitant Medication (CM) Changes ⁷	X	X	X

¹Screening and Baseline may occur on the same day. If this occurs, lesion count and review of inclusion/exclusion criteria will only occur once. If two members of the same household qualify for study participation, they must be randomized on the same day.

²All visit dates are in reference to Baseline, e.g. Week 2 occurs 14 days after Baseline Visit.

³Females 9 years of age and older.

⁴BOTE Inflammation Score will be assessed pre-dose at Baseline, and post-dose from Visit 3 through Visit 6. LSRs will be performed post-dose at each applicable visit.

⁵DLQI will be administered for subjects age 16 and older. The CDLQI will be administered for subjects ages 4 to age 16. If a subject turns 16 during the course of the study, the CDLQI will continue to be administered for consistency.

⁶Study drug application will occur in clinic at each study visit, from Baseline through Visit 5. Subjects will not apply the study drug at home on days where a study visit will occur.

⁷At Screening, subjects should be asked if any household members currently have MC. In addition to recording AE and CM changes, subjects should be asked if there are any new occurrences of MC in household members of subjects at each visit, except Screening and Day 2.

NOTE: Unscheduled visits are permitted as needed for medical reasons.

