6.2.2 Visit 1/Baseline (Day 1)

The following procedures must be performed and recorded at the Baseline visit. If Screening and Baseline visits occur the same day, procedures with an asterisk (*) should only be performed once and will be recorded as Baseline values.

1. Complete age-matched Dermatology Life Quality Index (DLQI) assessment, as applicable.
2. Perform a brief physical examination.
3. Perform lesion mapping and lesion count.*
4. Perform BOTE Inflammation Score (pre-dose).
5. Obtain urine pregnancy test, as applicable. If pregnancy test is positive, the subject may not participate in the study.
6. Update concomitant medication information.

7. Confirm eligibility and randomize subject.
8. Dispense subject diary and study drug.
9. Weigh and record study product tubes.
10. Instruct subject on dispensing, mixing, and application of study product and diary completion.
11. Have subject/caregiver apply first dose in clinic from kit assigned at randomization.
12. Complete Local Skin Reaction assessment approximately 30 minutes post dose.
13. Collect and record AE information for any AEs reported.

6.2.3 *Visit 2/Day 2 Telephone Contact*

The following procedure must be performed and recorded at the Day 2 telephone contact.

1. Contact subject to confirm how the subject is feeling.

6.2.4 *Visit 3/Week 2 (Day 15 ±3)*

The following procedures must be performed and recorded at the Week 2 visit.

1. Perform lesion mapping and update lesion map with location for any new lesions.
2. Assess for subject recurrence of MC.
3. Review study compliance.
4. Dispense subject diary.
5. Review dosing instructions and have subject/caregiver apply daily dose in clinic using the kit assigned at randomization.
6. Perform BOTE Inflammation Score (post-dose).
7. Complete Local Skin Reaction Assessment (post-dose).
8. Collect and record AE information for AEs reported.
9. Update concomitant medication information and confirm if any new occurrences of MC were reported in the subject's household.

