6.2.6 Visit 5/Week 8 (Day 57 ±5)

The following procedures must be performed and recorded at the Week 8 visit.

1. Obtain pregnancy test and evaluate results, as applicable. If pregnancy test is positive, the subject may continue in the study; however, study drug should be discontinued.
2. Perform lesion mapping and update lesion map with location for any new lesions.
3. Perform scarring/keloid assessment.
4. Weigh returned study drug and review study compliance.
5. Weigh, record, and dispense new supply of study product and dispense subject diary.

6. Review dosing instructions and have subject/caregiver apply daily dose in clinic using the newly dispensed kit.
7. Perform BOTE Inflammation Score (post-dose).
8. Perform Local Skin Reaction Assessment (post-dose).
9. Collect and record AE information for AEs reported.
10. Update concomitant medication information and confirm if any new occurrences of MC were reported in the subject's household.

6.2.7 *Visit 6/Week 12/ET (Day 85 ±5)*

The following procedures must be performed and recorded at the Week 12/ET1 visit.

1. Complete age-matched Dermatology Life Quality Index (DLQI) assessment, as applicable.
2. Obtain pregnancy test and evaluate results, as applicable.
3. Perform lesion mapping and update lesion map with location for any new lesions.
4. Perform scarring/keloid assessment
5. Perform a brief physical examination.
6. Subject/caregiver administer final dose of study drug from previously dispensed kit.
7. Perform BOTE Inflammation Score (post-dose).
8. Perform Local Skin Reaction Assessment (post-dose).
9. Weigh returned study drug and review study compliance.
10. Collect and record AE information for AEs reported.
11. Update concomitant medication information and confirm if any new occurrences of MC were reported in the subject's household.

6.2.8 *Visit 7/Week 16 and Visit 8/Week 20 (Day 113 +/- 7 days; Day 141 +/- 7 days)*

The following procedures must be performed and recorded at the Week 16 and Week 20 visits. It is expected that these visits should be done by telephone.

1. Collect and record information for new and ongoing AEs, including recurrence of MC.
2. Update concomitant medication information.

6.2.9 *Visit 9/Week 24 (Day 169 +/- 7 days)*

The following procedures must be performed and recorded at the Week 24 visit.

1. Perform scarring/keloid assessment.
2. Collect and record information for new and ongoing AEs, including subject recurrence of MC.

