7.2 Safety Assessments

7.2.1 *Physical Exam*

A brief physical examination will be performed to evaluate objective anatomic findings. This physical examination will be performed at Baseline and at Week 12/ET1. Any clinically significant changes in the physical exam from baseline will be recorded as AEs.

7.2.2 *Pregnancy Testing*

Urine pregnancy testing for females 9 years of age and older will be collected at Screening, Baseline, Week 4, Week 8 and Week 12/ET1. In addition to having a negative UPT at Baseline, before the first application of study drug, females 9 years of age and older must be willing to use an acceptable form of birth control during the study. The following are considered acceptable methods of birth control for this study: abstinence with a documented acceptable method of birth control if the subject becomes sexually active, oral contraceptives, contraceptive patches, contraceptive implant, vaginal contraceptive, double-barrier methods (e.g., condom and spermicide), contraceptive injection, Intrauterine Device (IUD), hormonal IUD, permanent contraception, same sex partner or partner who has had a vasectomy. Tubal ligation is not considered to be surgical sterilization; women with tubal ligations will be required to complete UPTs at the required timepoints.

7.2.3 *BOTE Inflammation Score*

Inflammatory reactions around the MC has been associated with imminent resolution of MC (sometimes referred to as “beginning-of-the-end” [“BOTE”] signs). In most cases, clinical features can differentiate between BOTE and LSR. BOTE may be associated with itching, but not pain. BOTE is usually asymptomatic, self-limited, localized to individual MC lesions, and does not require discontinuation of study treatment or additional treatment.

Investigators will assess the treatment area at each scheduled visit and use their medical judgement to differentiate between BOTE and LSRs. The BOTE Inflammation Score will be recorded at each visit. BOTE should not be considered an AE since this is part of normal disease progression.

BOTE Inflammation Score

Score	Global Assessment	Description
0	No inflammation	No evidence of local inflammation
1	Mild	Minimal erythema and/or edema
2	Moderate	Definite erythema and/or edema with or without hemorrhagic crusting
3	Severe	Erythema and edema with definite hemorrhagic crusting
4	Very Severe	Strong reaction spreading beyond the treated area, bullous reaction, erosions

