12. OTHER ANALYSES

The following analyses of BOTE vs lesion count/complete clearance will be presented:

- Percent change from Baseline at Week 12 in relation to the highest BOTE score during treatment.
- Complete clearance at Week 12 in relation to the highest BOTE score during treatment.

- Percent change from Baseline at each visit in relation to BOTE score at Week 2.
- Complete clearance at each visit in relation to BOTE score at Week 2.

In these analyses, the BOTE scores will be analyzed in the ITT Population as follows:

1. Dichotomized:

- a. Score of 0 or 1: No to Mild
- b. Score of 2, 3, or 4: Moderate to Very Severe

A shift table comparing the baseline BOTE score to each scheduled postbaseline assessment will be presented for the Safety Population.

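### BOTE is scored before the dose at Baseline but after the in-clinic dose at Weeks 2 to 12, so an immediate reaction to the gel can be scored as BOTE and can distort the BOTE displays

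*Combined protocol and SAP*

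**What the plan says.** Protocol Table 1, footnote 4, sets the timing: BOTE "will be assessed pre-dose at Baseline, and post-dose from Visit 3 through Visit 6". The visit lists follow it. Section 6.2.2 puts BOTE before the first dose. Sections 6.2.4 to 6.2.7 (Weeks 2, 4, 8 and 12) each carry the item "Perform BOTE Inflammation Score (post-dose", listed after the in-clinic application.

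LSR is handled uniformly: "LSRs will be performed post-dose at each applicable visit", Baseline included. At Baseline the interval is stated: "Complete Local Skin Reaction assessment approximately 30 minutes post dose". No interval is stated for BOTE at Weeks 2 to 12.

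To keep the two scores apart, section 7.2 asks investigators to "use their medical judgement to differentiate between BOTE and LSRs".

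The latest SAP version uses BOTE in three ways:

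- Section 12, shift table: "A shift table comparing the baseline BOTE score to each scheduled postbaseline assessment will be presented for the Safety Population".
- Section 12, displays against lesion outcome, cut at a score of 2. These use the highest score during treatment or the Week 2 score, for example "Complete clearance at each visit in relation to BOTE score at Week 2".
- Section 13.3, where a moderate BOTE score after Baseline is one criterion for an event of special interest.

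The SAP repeats that the Baseline score is pre-dose. It does not say when BOTE is taken relative to the dose at later visits, and it has no rule for the difference.

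**The concern.** BOTE is meant to capture inflammation that signals resolution of the lesions, as distinct from a reaction to the product. A pre-dose Baseline score suits that purpose. After Baseline, the score is taken once the gel has been put on the same lesions and about 1 cm of skin around them. Any quick reddening or swelling is then present when BOTE is graded.

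Three outputs are at stake. The shift table may show worsening that is only a change in measurement conditions. The BOTE-versus-clearance displays may understate how well early inflammation predicts clearance. The events-of-special-interest summary may count reactions to the gel as moderate BOTE. Because section 7.2.3 says BOTE is not an adverse event, the label given to a reaction also affects how it is reported.

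**Working it through.** The plan gives no figure on this point to reproduce. The check sets the passages side by side, then illustrates the possible size.

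**1. Timing**

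| Score | Baseline | Weeks 2, 4, 8 | Week 12 |
|---|---|---|---|
| BOTE | pre-dose | post-dose, no interval | post-dose, but see step 5 |
| LSR | post-dose, about 30 minutes | post-dose | post-dose |

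LSR compares like with like across visits, apart from the unstated interval. BOTE does not.

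**2. Overlap of signs.** BOTE grades 1 to 3 (section 7.2.3) use erythema, edema and hemorrhagic crusting. Grade 4 adds spread beyond the treated area, bullae and erosions. The LSR table (section 7.2.4) scores erythema, swelling, crusting, vesiculation and erosion, with spread outside the treatment area at grade 4 for several items. Section 4.1 also says that LSR features are rated with the BOTE score, which blurs the line further.

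**3. Is an early reaction plausible?** The protocol plans an LSR rating about 30 minutes after the first dose and a Day 2 call about early dose reactions. Section 1.1.4 names administration site reactions as the only adverse events clearly associated with SB206 in the Phase 2 molluscum study. It gives no rate for reactions within a visit.

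**4. Illustration for the Week 2 display, SB206 arm.** All inputs are assumed except the 36% overall clearance, which is the planned 18% vehicle rate plus the 18-point difference.

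- b = 0.20, share with true BOTE of 2 or more
- c1 = 0.50, Week 12 clearance with it
- c0 = (0.36 − 0.20 × 0.50)/0.80 = 0.325, clearance without it
- x = share of true negatives pushed to 2 or more by an immediate reaction *and* scored as BOTE, assumed unrelated to clearance

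Share scored 2 or more = b + (1 − b)x

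Clearance among them = [b·c1 + (1 − b)·x·c0] / [b + (1 − b)x]

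Observed difference = that clearance − c0 = (c1 − c0)·b / [b + (1 − b)x]

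| x | Scored 2 or more | Clearance among them | Difference from 32.5% |
|---|---|---|---|
| 0% | 20.0% | 50.0% | 17.5 points |
| 5% | 24.0% | 47.1% | 14.6 |
| 10% | 28.0% | 45.0% | 12.5 |
| 20% | 36.0% | 42.2% | 9.7 |
| 40% | 52.0% | 39.2% | 6.7 |

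The second column bears on the shift table. The share scored 2 or more after Baseline rises by 0.8x, that is by 4, 8, 16 or 32 points.

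A second assumed set (c1 = 0.50, c0 = 0.25, true odds ratio 3.0) shows the dependence on prevalence. At x = 5%, 10%, 20% and 30% the odds ratio is 2.54, 2.25, 1.91 and 1.71 when b = 20%, and 2.80, 2.63, 2.38 and 2.19 when b = 40%.

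**5. Subjects not dosed at the visit.** Subjects who stopped treatment for clearance, or who are on a drug holiday, have no in-clinic dose to be scored after. Their scores come from a different state, and for those who cleared, that state depends on the outcome. At Week 12 the state is unclear for everyone. Footnote 6 ends in-clinic dosing at Visit 5, while the Table 1 grid, section 6.1 and section 6.2.7 ("Subject/caregiver administer final dose of study drug from previously dispensed kit") include a Week 12 application.

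**The case against.** The strongest reply is that the protocol foresees the confusion. It gives features for telling the two apart: BOTE is confined to individual lesions and usually without symptoms, while LSR is more diffuse, with significant itch or tenderness. LSR is scored separately at the same visits. If investigators separate them perfectly, x is zero and only the formal mismatch remains. This stands to the extent that contamination is possible, not established. It does not remove the problem, because overlapping signs are judged at the same moment on freshly treated skin.

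A second reply also stands. Dosing is daily, so a pre-dose score at Week 2 would still follow about two weeks of gel. Moving the score removes only the same-visit effect.

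A reader might infer more than the documents support:

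- *The mismatch with Baseline carries into the clearance displays.* It does not. They use the Week 2 or highest score, not change from Baseline. Their risk is contamination.
- *Only the SB206 arm is affected.* Vehicle gel with hydrogel goes on the same skin, and nothing says it causes no immediate redness. More often on SB206 is plausible; exclusively is not shown.
- *BOTE is the trial's only early pharmacodynamic marker.* No section says so. BOTE is listed among the safety assessments, and lesion counts are taken from Week 2.
- *A post-dose BOTE adds nothing to safety.* SAP section 13.3 uses it as a criterion in its own right.
- *Stopping for clearance distorts the Week 2 score.* Treatment is planned for at least 4 weeks, so planned stopping bears on later visits. A drug holiday could still affect Week 2.

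**Conclusion.** The timing difference is real, stated consistently in the protocol, and not addressed in the SAP. The shift table compares pre-dose with post-dose scores. The clearance displays and the events-of-special-interest summary can be contaminated by same-visit reactions, and subjects not dosed at a visit are scored in a different state from the rest.

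The size is unknown. The range in the working, from no effect to a fall from 17.5 to 6.7 points, rests on assumed prevalence, clearance and misclassification, and on misclassification being unrelated to clearance. It shows direction and sensitivity and is not an estimate.

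The reach is limited to supportive BOTE displays and one safety summary. The primary and secondary endpoints are based on lesion counts and are unaffected. The case for acting is that the artefact is avoidable at almost no cost.

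**What to change.** Amend footnote 4 and the procedure lists in sections 6.2.4 to 6.2.7 so that BOTE is scored before any in-clinic application at every visit, as at Baseline. Keep LSR post-dose. The cost is protocol wording and a change of order within existing visits, with no added procedure or visit. Carry-over from earlier daily doses remains and should be acknowledged when the displays are interpreted.

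If data are already collected, flag for each BOTE score whether a dose preceded it at that visit. Label the shift table as pre-dose Baseline against post-dose follow-up, and state in the other BOTE displays and the events-of-special-interest summary that the scores are post-dose. The cost is one derived flag and some footnotes.

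Separately, footnote 6 contradicts the Table 1 grid, section 6.1 and section 6.2.7 on whether a dose is applied in clinic at Week 12. These passages must be reconciled.
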